5.3.5. Secondary Endpoint Analysis

5.3.5.1. Key Confirmatory Secondary Endpoint

The key confirmatory secondary endpoint in this study is the change from baseline in modified van der Heijde-Sharp (vdH-S) score at Week 24, under the subgroup of participants without high baseline radiographic variability, as well as over the entire mFAS.

5.3.5.1.1. Definition of Endpoint

The vdH-S score is an original vdH-S score (van der Heijde 1992) modified for PsA. The modification for PsA includes addition of distal inter-phalangeal (DIP) joints of both hands scored for erosions and joint space narrowing (JSN), and assessments of radiographic features known as “pencil in cup” (PIC) and “gross osteolysis” (GO) that are specific to PsA. The vdH-S score is a measurement of progression in structural damage. It is the sum of joint erosion score and JSN score. The erosion score and JSN score, respectively, is a measurement of 2 types of structural damage.

The **joint erosion score** is a summary of erosion severity in 40 joints of the hands (20 joints per hand) and 12 joints in the feet (6 in each foot). Each joint is scored according to the surface area involved, from 0 to 5, with 0 indicating no erosion and 5 indicating complete collapse of bone. To identify the presence of PIC and GO in the hands, a modification of erosions scores of 6 and 7 are applied by IRC radiologists. For joints with one of these abnormalities, the maximum score of 5 will be applied. To identify the presence of PIC and GO in the feet, a modification of erosions scores of 11 and 12 are applied by IRC radiologists. For joints with one of these abnormalities the maximum score of 10 will be applied. Therefore, the maximum erosion score for a hand joint is 5 and the maximum erosion score for hands is 200. Because each side of a foot joint is graded on the scale of 0 to 5, the maximum erosion score for a foot joint is 10 and the maximum erosion score for feet is 120. Thus, the maximal **erosion score (i.e., hand erosion score + foot erosion score)** is 320.

The **joint space narrowing score** summarizes the severity of JSN in 40 joints in the hands and 12 joints of the feet. Assessment of JSN is scored from 0 to 4, with 0 indicating no JSN and with 4 indicating absence of a joint space, presumptive evidence of ankylosis or complete luxation. Therefore, the maximum JSN score for a hand joint is 4 and the maximum JSN score for hands is 160. The maximum JSN score for a foot joint is 4 and the maximum JSN score for feet is 48. Thus, the maximal **JSN score (i.e., hand JSN score + foot JSN score)** is 208.

The maximal erosion score of 320 combined with the maximal JSN score of 208 gives worst possible **modified vdH-S score (ie, erosion score + JSN score)** of 528.

Joint Evaluability Rules specified in Section 6.10 for joint evaluation will be applied to those joints with surgery/joint replacement or with radiographically insufficient data for reading. For

participants with incomplete set of evaluable joints, Erosion and JSN Score Adjustment Rules described in Section 6.10 will be applied to determine the ultimate **sub-scores (i.e., scores of hand erosion, hand JSN, foot erosion, and foot JSN)** for each reader. A composite score [including erosion, JSN, **hand (i.e., hand erosion + hand JSN)**, **foot (i.e., foot erosion + foot JSN)**, and modified vdH-S scores] will be set to missing if any of its corresponding sub-scores is missing.

Confirmation will occur when the 2 primary readers do not agree with each other with respect to change from baseline in modified vdH-S score at any post-baseline visit. The criteria for triggering confirmation can be found in Section 6.10. **Note** that the criteria for triggering confirmation should be determined based on the observed data (i.e., data without application of those data handling rules specified in Section 5.3.2). Section 6.10 outlines the rules to select which 2 readers' scores to be used in the analysis for participants with confirmation.

The final scores or sub-scores at each visit are the average of corresponding scores from the 2 primary readers for a participant without confirmation, the 2 primary readers for a participant with confirmation but both primary readers equally distant from confirmation reader, and the confirmation reader and the primary reader closest to the confirmation reader otherwise for a participant with confirmation.

Change from baseline in modified vdH-S score measures the change in progression of structural damage, where a negative change indicates an improvement and a positive change indicates a worsening.

5.3.5.1.2. Estimand

Adjusted Treatment Policy Estimand (Primary)

This estimand is defined by the 5 components:

- **Population:** Participants with active PsA who are biologic naïve
- **Treatment:**
 - Placebo
 - Guselkumab
- **Variable:** change from baseline in modified vdH-S score at Week 24 irrespective of background PsA medication or adherence to study intervention, in the hypothetical situation where Natural Disaster or Major Disruption and associated ICE categories 4 and 5 did not occur.
- **Intercurrent Events:**
 1. Discontinued study intervention injections due to any reason **except** due to Natural Disaster or Major Disruption.
 2. Initiated or increased the dose of non-biologic DMARDs (MTX, SSZ, HCQ, LEF) or oral corticosteroids over baseline for PsA.
 3. Initiated protocol prohibited medications/therapies for PsA.

4. Discontinued study intervention injections due to Natural Disaster or Major Disruption.
5. Severe treatment non-compliance due to Natural Disaster or Major Disruption, defined as ≥ 2 doses of study intervention missed due to Natural Disaster or Major Disruption.
- **Population level summary:** difference in mean changes (as per definition of **Variable** above) between guselkumab group and placebo group.

*Note that in the context of ICEs and missing data, the following are defined:

1. **Natural Disaster: site closure**, site access restrictions, or lockdowns caused by COVID-19.
2. **Major Disruption:** the disruption involving Ukraine and neighboring countries/territories beginning February 24, 2022

This estimand examines the difference in mean change in modified vdH-S score after 24 weeks irrespective of background PsA medication or adherence to study intervention, in the hypothetical scenario where Natural Disaster or Major Disruptions did not occur, between each guselkumab group individually versus placebo, amongst participants with active PsA who are biologic naïve.

Treatment Policy Estimand (*Supplementary*)

This estimand is defined by the 5 components:

- **Population:** same as adjusted treatment policy estimand
- **Treatment:** same as adjusted treatment policy estimand
- **Variable:** change from baseline in modified vdH-S score at Week 24 irrespective of background PsA medication or adherence to study intervention.
- **Intercurrent Events:** the definition of the 5 categories of ICE, and the definition of Natural Disaster and Major Disruption, are the same as for the Adjusted Treatment Policy Estimand.
- **Population level summary:** difference in mean changes (as per definition of **Variable** above) between guselkumab group and placebo group.

This estimand examines the difference in mean change in modified vdH-S score after 24 weeks irrespective of background PsA medication or adherence to study intervention, between each guselkumab group individually versus placebo, amongst participants with active PsA who are biologic naïve.

5.3.5.1.3. Analysis Methods

The main analysis of the key confirmatory secondary endpoint will be analyzed at Week-24 DBL based on the Adjusted Treatment Policy Estimand.

In the primary efficacy analysis, data from all participants in mFAS(Section 4.2) will be analyzed according to randomized intervention group regardless of the treatment actually received.

ICE Strategies

For the Adjusted Treatment Policy Estimand, the treatment policy strategy will be used for ICEs 1 to 3, wherein all observed data collected for the endpoint is used. The occurrence of the intercurrent event is irrelevant: the value for the variable of interest is used regardless of whether or not the intercurrent event occurs.

The hypothetical strategy will be used for ICEs 4 and 5, wherein observed data collected after the ICE will not be used and will be assumed to be MAR, then imputed using FCS MI.

For participants experiencing multiple ICEs, an ICE in categories 4 and 5 will supersede an ICE in categories 1 to 3.

Handling Rules for Missing Data for Adjusted Treatment Policy Estimand

After ICE strategies have been implemented, remaining missing data will be handled as follows:

- **Missing data for any reason** will be imputed using FCS MI as described in Section 5.3.2.

Analysis Testing

Data from unscheduled visits which do not fit into the analysis window (Section 5.1.1.2) will not be used. Treatment comparisons for each imputation data set will be based on an ANCOVA model adjusted for baseline score and randomization strata levels. The analysis results from the N imputation datasets will be combined, according to Rubin (Rubin 1987), and the p-value for testing the treatment difference will be obtained.

In order to control the overall Type 1 error rate, the key confirmatory secondary endpoint will be tested in a fixed sequence if both hypotheses of the primary endpoint are statistically significant.

3. Guselkumab 100 mg q4w SC is superior to treatment with placebo SC as measured by change from baseline in modified vdH-S score at Week 24
4. Guselkumab 100 mg at Week 0, Week 4, then q8w SC is superior to treatment with placebo SC as measured by change from baseline in modified vdH-S score at Week 24.

5.3.5.2. Sensitivity and Supplementary Analyses

1. **(Sensitivity Analysis 1)** To evaluate the robustness of the **Adjusted Treatment Policy Estimand** regarding the assumptions for missing data, two-dimensional tipping point analyses based on FCS MI imputed data will be performed to evaluate the deviation from the assumption of MAR for missing data (Section 5.3.2.1) using the same MI imputed dataset as that used for the main analysis. Note that data imputed as part of the ICE strategy (MI due to meeting ICEs 4 and 5) will be performed prior to the tipping point analysis. The same analyses method as that for the main analysis, will be fitted for each combination of deltas. The analysis results from the N imputation datasets will be combined, according to Rubin (Rubin 1987) and the p-value for testing the treatment difference will be obtained.

2. **(Sensitivity Analysis 2)** To assess the effect of including all randomized participants, even those from sites rendered unable to support key study operations due to Natural Disaster or Major Disruption, the same analysis as the main analysis will be performed on the FAS analysis set.
3. **(Sensitivity Analysis 3)** To assess the influence of outliers and extreme observations, a trimmed analysis will be performed. The same analysis method as for the main analysis, ANCOVA on multiply imputed data, will be performed on a subset of data where k% (k ranging from 1 to 10) of data are removed from the highest and lowest change scores of modified vdH-S in each intervention group.
4. **(Sensitivity Analysis 4)** To assess the influence of difficult to read radiographs. The same analysis method as for the main analysis, ANCOVA on multiply imputed data, will be performed on a subset of data where participants randomized to the HRV randomization strata are excluded.
5. **(Sensitivity Analysis 5)** An analysis similar to the main analysis, except replacing the randomization stratification factor in the ANCOVA analysis model with the baseline covariates: number of joints with erosion (numeric), log-transformed CRP (mg/dL, numeric), and oral corticosteroid use (Y/N).
6. **(Sensitivity Analysis 6)** To assess the impact of a narrower baseline window, the same analysis as the main analysis will be performed, but only participants with baseline and Week 24 observations within +/- 2 weeks of the expected assessment time, ie, study week -2 for baseline and study week 24 for Week 24 respectively, are included in the analysis.
7. **(Sensitivity Analysis 7)** To assess the impact of using the original analysis window, the same analysis as the main analysis will be performed, but both baseline and Week 24 observations within +/- 8 weeks of the expected assessment time, ie, study week -2 for baseline and study week 24 for Week 24 respectively, are included in the analysis.
8. **(Sensitivity Analysis 8)** To use all collected post-bl data even outside of the 2 week analysis window, a 2-step MI will be used for imputation: 1) Missing Week 24 data from participants with an x-ray measurement at baseline and a measurement post-baseline during the placebo controlled period will be imputed through a mixed effect linear growth curve (MLGC) model (see Section 6.13); 2) Other missing data will be imputed using the FCS regression method based on the imputed dataset from the 1st step. The 2-step MI will be applied only to the modified vdH-S score and not the erosion or JSON scores.
9. **(Sensitivity Analysis 9)** To assess the effect of excluding all Ukrainian participants from the analysis, as all sites in Ukraine have been impacted by Major Disruption (e.g., study intervention interruptions, temporary site closures, etc) to a larger or smaller extent. The same analysis as the main analysis will be performed on the mFAS-UKR analysis set.
10. **(Sensitivity Analysis 10)** As the Major Disruption has the potential to prevent SDV from taking place (e.g, due to site closure, site inaccessibility, etc), an analysis will be conducted to assess the impact by excluding affected participants. The same analysis as the main analysis will be performed on the mFAS analysis set, excluding participants for which expected SDV was not completed for data on or prior to Week 24.
11. **(Supplementary Analysis 1)** To support regulatory decision making, an analysis based on the **Treatment Policy Estimand** will be performed. The observed modified vdH-S score for participants will be used regardless of whether or not ICE criteria are met prior to Week 24,

and missing modified vdH-S score will be imputed using FCS MI under the assumption that data are MAR. The same analysis method as the main analysis will be performed. The analysis will be performed based on the mFAS-UKR analysis set.

12. **(Supplementary Analysis 2)** A two-dimensional tipping point analysis for the **Treatment Policy Estimand** will be performed. The observed modified vdH-S score for participants will be used regardless of whether or not ICE criteria are met prior to Week 24, and missing modified vdH-S score will be imputed using FCS MI under the assumption that data are MAR. Varying pairs of deltas will then be added to the imputed values (Section 5.3.2.1) to evaluate deviation from the assumption of MAR for missing data. The same analysis method as in the main analysis of this endpoint will be applied for each pair of deltas. The analysis will be done for pairs of delta values including scenarios where participants on guselkumab have worse outcomes than participants on placebo. This analysis will be performed based on the mFAS-UKR analysis set.

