For most continuous endpoints where any portion of the missing data is imputed using MI (see Section 6.11 for technical details), treatment comparisons will be performed using an **Analysis of Covariance (ANCOVA)** model on each of the imputation sets. The estimate of the mean change from baseline is the average of the mean change taken over all the MI data sets. The estimate of the variance of the mean change from baseline is the weighted sum of the average within-imputation variance and the between-imputation variance. The confidence interval for the mean change from baseline uses critical values from the t-distribution. The treatment difference between each guselkumab group versus the placebo group will be tested for each imputation dataset and then the analysis results across all imputation datasets will be combined. The treatment difference in the change from baseline is estimated by the average of the treatment differences over the MI data sets. The estimate of the variance of the treatment difference in the change from baseline is the weighted sum of the average within-imputation variance and the between-imputation variance, under the assumption of homogeneity of variance between intervention groups for performing ANCOVA within each imputation dataset. The confidence interval is based on the critical values from the t-distribution. The large number of observations in our data imply that the critical values from the t-distribution are almost identical to the critical values from the standard normal distribution.

The ANCOVA model will be based on the original scale and will include intervention group, baseline score, and randomization strata levels as the explanatory factors. The model will include data from all the 3 intervention groups.

For analyses where all missing data is imputed only a single time (e.g., change=0 for all missings) or not imputed with the missing assumed MCAR, treatment comparisons will generally be performed using ANCOVA.

For endpoints where any portion of the missing data is not imputed, but still needs to be accounted for under MAR assumptions, the **Mixed-Effect Model Repeated Measures (MMRM)** model will be used (for more details see Section 6.13).

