Sensitivity Analysis 3/ mFAS/ Adjusted Treatment Policy	ICEs 4 and 5, data not used, but rather imputed using FCS MI Missing data assumed MAR, imputed via FCS MI	
 Trimmed analysis: k% (k ranging from 1 to 10) of data are removed from the highest and lowest change scores of in each intervention group. Summarized descriptively at each level of k Treatment comparisons including p-value from combining ANCOVA model treatment difference across multiply imputed datasets, separately at each level of k

Table 8: Summary of Analyses Related to the Key Confirmatory Secondary Endpoint of Change from Baseline in Modified vdH-S Score at Week 24

Analysis/Population/Estimand	ICE/Missing data imputation	Additional notes
Sensitivity Analysis 4/ mFAS excluding HRV participants/ Adjusted Treatment Policy	ICEs 4 and 5, data not used, but rather imputed using FCS MI Missing data assumed MAR, imputed via FCS MI	
 Analysis for non-HRV participants Summarized descriptively Treatment comparisons including p-value from combining ANCOVA model treatment difference across multiply imputed datasets
Sensitivity Analysis 5/ mFAS/ Adjusted Treatment Policy	ICEs 4 and 5, data not used, but rather imputed using FCS MI Missing data assumed MAR, imputed via FCS MI	
 Summarized descriptively Treatment comparisons including p-value from combining ANCOVA model treatment difference across multiply imputed datasets.
Sensitivity Analysis 6/ mFAS excluding participants with baseline assessment outside +/- 2 weeks of Week -2/ Adjusted Treatment Policy	ICEs 4 and 5, data not used, but rather imputed using FCS MI	
 Summarized descriptively Treatment comparisons including p-value from combining ANCOVA model treatment difference across multiply imputed datasets
Sensitivity Analysis 7/ mFAS/ Adjusted Treatment Policy	ICEs 4 and 5, data not used, but rather imputed using FCS MI	
 Analysis window using +/- 8 weeks for both bl and Week 24 Summarized descriptively Treatment comparisons including p-value from combining ANCOVA model treatment difference across multiply imputed datasets

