3	Proportion of participants with change ≤ 0 from baseline in modified vdH-S erosion score, JSN score at Week 24	mFAS	FCS MI for MAR	
 Summarized descriptively Combined CMH statistic^a across imputation sets for p-value Response rates, and treatment difference in response rates and 95% CI, based on combined results across imputation sets.
4	Proportion of participants with change ≤ 0.5 from baseline in modified vdH-S score at Week 24	mFAS	FCS MI for MAR	
 Summarized descriptively Combined CMH statistic^a across imputation sets for p-value Response rates, and treatment difference in response rates and 95% CI, based on combined results across imputation sets.
5	Proportion of participants with change ≤ 0.5 from baseline in modified vdH-S erosion score, JSN score at Week 24	mFAS	FCS MI for MAR	
 Summarized descriptively Combined CMH statistic^a across imputation sets for p-value Response rates, and treatment difference in response rates and 95% CI, based on combined results across imputation sets.
6	Proportion of participants without radiographic progression (based on SDC) at Week 24	mFAS	FCS MI for MAR	
 Summarized descriptively Combined CMH statistic^a across imputation sets for p-value Response rates, and treatment difference in response rates and 95% CI, based on combined results across imputation sets.

Table 14: Summary of Estimands, Analysis Sets, Data Handling Rules, and Analysis Methods for Endpoints of Joint Structural Damage

	Endpoint	Analysis Set	Missing Data Rules	Analysis Methods
7	Proportion of participants without radiographic erosion progression, radiographic JSON progression (based on SDCs) at Week 24	mFAS	FCS MI for MAR	
 Summarized descriptively Combined CMH statistic^a across imputation sets for p-value Response rates, and treatment difference in response rates and 95% CI, based on combined results across imputation sets.
8	Change from baseline in modified vdH-S by region and type of damage at Week 24	mFAS	-	
 Summarized descriptively
9	Proportion of participants with pencil in cup or gross osteolysis deformities at Baseline and Week 24	mFAS	-	
 Summarized descriptively

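### Sensitivity Analysis 3 trims outcome tails within each arm but keeps the ordinary ANCOVA standard error, so its p-values and confidence intervals are too favourable

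*SAP*

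**What the plan says.** SAP 5.3.5.2 describes Sensitivity Analysis 3 as a trimmed analysis of the key confirmatory secondary endpoint, the Week 24 change in modified vdH-S score. It "will be performed on a subset of data where k% (k ranging from 1 to 10) of data are removed"; the removals are made at both ends of the outcome distribution, arm by arm. The method applied to what remains is unchanged: "The same analysis method as for the main analysis, ANCOVA on multiply imputed data".

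The main analysis (SAP 5.3.5.1.3) fits, in each imputed dataset, an "ANCOVA model adjusted for baseline score and randomization strata levels" and pools by Rubin's rules. SAP 5.3.1 gives the variance: "The estimate of the variance of the treatment difference in the change from baseline is the weighted sum of the average within-imputation variance", together with the between-imputation variance, assuming equal variances across arms.

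Table 8 (SAP 5.3.5.5) commits to inference at each trimming level: "Treatment comparisons including p-value from combining ANCOVA model treatment difference across multiply imputed datasets, separately at each level of k". It also plans descriptive summaries at each k.

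No section gives a trimmed-mean, winsorized or bootstrap standard error. None says whether k% is removed from each tail or in total, or whether trimming is repeated within each imputed dataset.

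**The concern.** Participants are dropped because of their outcome. Removing both tails shrinks the residual variance, and ordinary ANCOVA then treats the remainder as a plain random sample. The sampling variance of a trimmed mean depends on the winsorized variance of the full sample, which is larger. The reported standard error is therefore too small, increasingly so as k rises.

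The table exists to show whether the result depends on a few extreme scores. If its test rejects too easily, a result that stays significant from k=1 to k=10 says less about robustness than it appears to, and a main result just short of significance can become significant through trimming alone.

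**Working it through.** **1. Reproduce the SAP's planning figures.** SAP 3.1.2 models the change score as 15% (or 25%) exact zeros and otherwise normal; in the base case the normal part has mean 1.33 (placebo), 0.29 (q4w) or 0.53 (q8w) and SD 3.4. Placebo check: mean 0.85 × 1.33 = 1.13; SD √[0.85 × (3.4² + 1.33²) − 1.13²] = 3.17, stated as 3.2. With 350/250/350 participants, 10,000 simulations and ANOVA on van der Waerden scores, power came to 92.3% (q4w) and 80.2% (q8w), against the stated 92% and 80%. The model is reproduced.

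**2. Size of the error in theory.** With a fraction g removed from each tail of n observations:

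- true variance of the trimmed mean = winsorized variance / [(1 − 2g)² n]
- ordinary variance = variance of the retained data / [(1 − 2g) n]

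For a standard normal outcome and g = 0.10, the ordinary value is 0.438/0.8 = 0.547 (per 1/n) and the true value is 0.679/0.64 = 1.06. The standard error is too small by √(1.06/0.547) = 1.39, and a nominal 5% test rejects when |Z| > 1.96/1.39 = 1.41, about 16% of the time. For the SAP's mixture with 15% zeros and complete data, the factor is 1.24 at 5% per tail (error 11.4%) and 1.43 at 10% per tail (17.0%).

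**3. Simulation of the planned analysis with no treatment effect.** 350/250/350; 15% or 25% zeros, otherwise normal (1.33, SD 3.4) in every arm; three-arm ANCOVA with baseline and four strata; 20 imputations; trimming by arm inside each imputed dataset; Rubin pooling; 6,000 datasets per setting. Assumed, because the documents do not give them: 5% or 10% missing, strata shares, the baseline distribution and small prognostic slopes. The total change score was imputed rather than the four component scores.

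Rejection rate of the nominal 5% test (range over settings and both comparisons):

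| k | k% in total | k% per tail |
|---|---|---|
| 0 | 4.5% to 5.5% | 4.5% to 5.5% |
| 1 | 5.0% to 6.1% | 5.6% to 6.9% |
| 2 | 5.6% to 6.9% | 6.6% to 8.1% |
| 5 | 7.0% to 8.4% | 9.3% to 10.9% |
| 10 | 9.3% to 10.9% | 13.4% to 16.1% |

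At k=10 the reported standard error is 0.81 to 0.85 (total) or 0.71 to 0.76 (per tail) of the true value, so a 95% interval covers about 89% to 91% or 84% to 87%.

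**4. Dependence on assumptions.** A separately programmed simulation gave, at k=10 (total; per tail):

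- 15% zeros, no missing data: 11.5%; 17.2%
- 15% zeros, 5% to 15% missing: 9.3% to 10.7%; 12.5% to 15.7%
- 15% zeros, 20% missing: 9.1% to 9.3%; 11.9% to 12.5%
- 60% zeros, 10% missing: 11.9% to 12.5%; 16.7% to 17.1%
- t tails with 4 df, 10% missing: about 10%; 13% to 14%

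The untrimmed test stayed at 4.8% to 5.6% throughout, so the trimming is the cause.

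**5. A valid standard error removes the excess.** A bootstrap repeating the trimming in each resample (15% zeros, 1,200 null datasets per missingness level, 10 imputations, 60 resamples) brought 10% per tail from 14.2% to 15.7% down to 4.8% to 5.2%. A closed-form winsorized-variance standard error, tested on an unadjusted two-arm comparison, gave about 4% to 6% at all trims tried.

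**6. Effect on the reading.** Of 232 comparisons significant by chance in the main analysis, 99% to 100% stayed significant with the ordinary standard error. With the bootstrap, 77% to 78% did at 10% per tail. Null main p-values of 0.05 to 0.10 fell below 0.05 at k=10 in 72% to 78% (total) or 85% to 88% (per tail).

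**The case against.** The strongest reply is about consequence. This is one of ten sensitivity and two supplementary analyses of the endpoint and lies outside the fixed sequence of SAP 5.3.3.2. No claim rests on it. Influence of outliers is first a question of how the estimate moves with k, and the trimmed estimates answer that. Table 14 also plans Week 24 comparisons, such as "Proportion of participants without radiographic progression (based on SDC) at Week 24", that bear on extreme values and are not affected. All of this stands and limits the weight of the point. The rejection rates are the size of this table's own test: the chance that the main and trimmed tests are both falsely significant cannot exceed the main test's 5%.

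The ranges are not bounds. The missing rate is assumed, and more zeros raise the error: with 60% exact zeros and complete data, k=10 gave about 16% (total) and 25% (per tail). Protocol 4.3 reports that about two thirds of participants in the earlier study did not progress, though that need not mean a change of exactly zero. The size varies; the direction does not.

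The 99% figure comes from a model without outliers. With 2% to 4% of placebo participants given a large extra change under the null (complete data), the ordinary analysis kept significance in only 33% to 41% (5% per tail) or 37% to 45% (10% per tail), and the estimate fell by roughly two thirds, so the table often exposes an outlier-driven result. A gap remains, however: in a run with 3% placebo outliers, the ordinary standard error kept 42% to 45% and a valid one 18% to 22%.

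**Conclusion.** The concern holds: the inference in Sensitivity Analysis 3 is wrong as written. Trimming on the outcome within arm, combined with an unadapted ANCOVA variance, gives intervals that are too narrow and p-values that are too small. Under the SAP's planning mixture with 5% or 10% assumed missing, the nominal 5% test at k=10 runs at about 9% to 11% or 13% to 16%, depending on how k% is read; the effect is slight at k=1. These are illustrations that move with the outcome distribution and missingness, but inflation at k=10 appeared in every setting tried.

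The scope is one sensitivity table. It should be corrected, but it does not threaten the confirmatory result or the usefulness of the trimmed estimates. Even a corrected version is only a limited check, since most chance findings survive it when no outliers are present.

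**What to change.** Keep the trimming levels and the trimmed ANCOVA estimates, and do one of the following.

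- **(a) Report descriptively.** Give the trimmed estimates at each k without p-values or model-based intervals. This takes two SAP sentences and no new programming. It gives up inference in this table.
- **(b) Use a standard error valid for trimming.** For example, bootstrap within each imputed dataset, repeat the trimming in every resample, and pool by Rubin's rules. This takes two or three sentences and a programming loop over imputed datasets and levels of k, with no new data. A winsorized-variance standard error is lighter to compute but was checked only without covariates and would need adapting to the ANCOVA.

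The price of (b) is less favourable p-values. In 500 runs under the planned effects with 5% missing, apparent power at 10% per tail fell from 96% to 89% (q4w) and from 88% to 72% (q8w), against 92% and 77% untrimmed.

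In either case, state whether k% is per tail or in total, and that trimming is done within each imputed dataset. A normal-score ANCOVA could be added, but it does not estimate the mean difference and does not replace either option.
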